3.2 Treatment Variables

Concomitant Medication Review. Subjects will be asked about their use of medications (over the counter and prescription) and substances that may alter subjects' response to the study medication. The Study Physician/Health Care Provider will advise as to whether other medications being taken are contraindicated and prescribe appropriate action from there (i.e., discontinuation of the study medication). The concomitant medication review will be completed at every study visit following the Intake.

Pill Count/Adherence. Medication adherence will be assessed by pill count at each study visit or telephone session [42]. We will assess patch use by participants' self-report and collect unused patches at the end of the week.

Side Effects. A checklist of side effects based on the product insert will be administered to participants at all study visits after the Intake. The frequency and severity of common side effects of RAM [43] and TN [30, 44] will be rated on a 0 (none) to 3 (severe) scale. An open-ended side effects question will also be included. Furthermore,

participants will receive written instructions to call the Health Care Provider/Study Physician should they experience any severe side effects or adverse events between study visits.

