Potential Risks of the Medication: The following are the common side effects that have been reported with ramelteon treatment: drowsiness, tiredness, dizziness, and nausea. All of these side effects have been mild and

transient in nature. These symptoms have occurred in approximately 3% of subjects in clinical trials (Takeda Pharmaceutical, 2005). Side effects will be assessed at baseline of each period and each subsequent visit (a total of 16 times throughout the study). The incidence of side effects is lower with the 8mg dose (as compared to the 16mg dose); which is the dose that has been selected in the proposed project.

In addition to the side effects mentioned above, other rare side effects of ramelteon have been reported:

- Severe anaphylactic and anaphylactoid reactions such as angioedema (swelling of the tongue and larynx), difficulty swallowing, vomiting, and throat closing.
- Abnormal thoughts and behavioral changes such as hallucinations, suicidal thoughts, bizarre behavior, agitation and mania, amnesia, and anxiety
- Complex behaviors such as "sleep-driving" and other behaviors (e.g., preparing and eating food, making phone calls)
- Hormone effects including decreased testosterone and increased prolactin

All of these side effects shall be queried using a side effects checklist as described above.

Stringent exclusion criteria are in place to limit the chance of these side effects. Additionally, participants will be informed about these possible side effects and be made aware to watch for any of these symptoms and report them as soon as possible to the research staff. All subjects will be instructed to take the study medication 30 minutes before going to bed. They will also be warned they should not drive or operate machinery after taking ramelteon and that they should limit their consumption of alcohol. All side effects will be closely monitored and the study physician consulted should moderate or severe side effects be reported. In case any participant experiences severe side effects or an adverse event, they will be encouraged to contact the study physician ([name]) and study PI ([name]) immediately for appropriate intervention. The study physician's emergency contact numbers shall be on the medication blister pack, the study consent form, and a study brochure all participants will be provided with once they enroll into the study.

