4.2 Adverse Event Reporting and Monitoring

Adverse Event (AE)

An Adverse Event (AE) is a subcategory of the broader category of "Unanticipated Problems Posing Risk to Subject or Others." An adverse event is defined as:

- Any unfavorable or unintended sign (including an abnormal laboratory finding), symptom, or disease occurring at any stage of the study
- Abnormal results of diagnostic procedures are considered to be adverse events if the abnormality:
 - results in study withdrawal
 - is associated with a serious adverse event
 - is associated with clinical signs or symptoms
 - leads to additional treatment or to further diagnostic tests
 - is considered by the investigator to be of clinical significance
- May include an exacerbation of a pre-existing condition, intercurrent illness or injury, drug interaction, drug overdose, failure of expected action or significant worsening of the disease under study
- An event that may compromise the rights, safety, or welfare of research subjects

Any event that could be characterized by the definitions above is an AE whether or not considered related to the study or product.

Serious Adverse Event (SAE)

Adverse events are classified as serious or non-serious. A **serious adverse event** is any AE that is:

- fatal
- life-threatening
- requires or prolongs hospital stay
- results in persistent or significant disability or incapacity
- a congenital anomaly or birth defect
- an important medical event

Important medical events are those that may not be immediately life threatening, but are clearly of major clinical significance. They may jeopardize the subject, and may require intervention to prevent one of the other serious outcomes noted above. For example, drug overdose or abuse, a seizure that did not result in in-patient hospitalization, or intensive treatment of bronchospasm in an emergency department would typically be considered serious.

All adverse events that do not meet any of the criteria for serious will be regarded as **non-serious adverse events**.

Adverse Event Reporting Period

The study period during which adverse events must be reported is the period from the initiation of any study procedures to the end of the study treatment follow-up. For this study, the study treatment follow-up is defined as 7 days following the last administration of study treatment. A compilation of any Adverse Events will be provided in the annual and final progress reports to NIDA.

Preexisting Condition

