- Unrelated - The AE is clearly NOT related to the intervention
- Unlikely - The AE is doubtfully related to the intervention
- Possible - The AE may be related to the intervention

- Probable - The AE is likely related to the intervention
- Definite - The AE is clearly related to the intervention

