4.3 Recording of Adverse Events

At each contact with the subject after the Intake, the study research assistant will seek information on adverse events by specific questioning using a side effect checklist and, as appropriate, by examination. Side effects will be monitored through a two-pronged approach. First, participants will complete a side effects checklist (SEC) at each study visit after the Intake reporting with a frame of reference since their last study visit. The SEC will assess the frequency and severity of common side-effects associated with ramelteon or TN treatment. These items will be rated by participants on a 0 (none) to 3 (severe) scale, and can be summed to provide an overall side effects index.

Second, trained staff will ask participants a non-structured, open-ended question (SEC Open-ended) at each study visit with a one week frame of reference to assess if participants are experiencing any additional symptoms or medical concerns that may be related to their participation in the study.

Research staff are trained to inquire (time of onset, nature of issue reported, possible relation to ramelteon/TN treatment, review of previously reported side effects or concerns, etc.) about any notable side effects or medical concern reported by participants. Any severe (or a pattern of moderate) side effects or notable medical concern will be reported to the Project Manager, Study Physician, and Principal Investigator to determine a course of action (e.g. continue to monitor, reduce medication, stop medication). This consult, including all relevant information, will be documented via email. The Study Physician is knowledgeable of side effects related to ramelteon/TN and is qualified to manage possible side effects.

Based on published reports using the 8mg dose of ramelteon and 21mg dose of TN we expect few side effects and we expect these side effects to be mild and transient in nature. However, in the unlikely event of an adverse event (AE) the study physician will determine the severity of the AE, the relationship of the event to the study drug and decide the course of action for the study subject. The study physician will determine the relationship of toxicity of the study medication as not related, possibly related, probably related, or definitely related using standard criteria.

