All adverse events occurring during each study period will be recorded. The clinical course of each event will be followed until resolution, stabilization, or until it has been determined that the study treatment or participation is not the cause. Serious adverse events that are still ongoing at the end of the study period must be followed up to determine the final outcome. Any serious adverse event that occurs after the study period and is considered to be possibly related to the study treatment or study participation will be recorded and reported immediately.

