- Report the event within 24 hours when the death is unforeseen (unexpected) and indicates participants or others are at increased risk of harm.
- Report the event within 72 hours, for all other deaths, regardless of whether the death is related to study participation.

For reportable deaths, the initial submission to the Penn IRB may be made by contacting the IRB Director or Associate Director. The AE/Unanticipated Problem Form is required as a follow up to the initial submission.

Reporting SAEs

• Penn Subjects (including subjects at networks, affiliates or investigator-initiated sites); All on-site grade 3 or higher AEs or ADRs regardless of attribution or expectedness will be submitted to the IRB within 30 days. SAEs or SADR for Penn subjects regardless of attribution or expectedness will be submitted to the IRB within 10 days. Reports will continue to be sent to the IRB for 90 days following the last date the subject received study treatment/therapy or was exposed to an investigational device. All unexpected deaths or deaths related to the study agent(s)/device(s) must be reported within 24 hours. All other deaths should be reported within 30 days.

Other Reportable events:

- For clinical drug trials, the following events are also reportable to the Penn IRB:
- Any adverse experience that, even without detailed analysis, represents a serious unexpected adverse event that is rare in the absence of drug exposure (such as agranulocytosis, hepatic necrosis, Stevens-Johnson syndrome).
- Any adverse event that would cause the sponsor to modify the investigators brochure, protocol or informed consent form, or would prompt other action by the IRB to assure protection of human subjects.

- Information that indicates a change to the risks or potential benefits of the research, in terms of severity or frequency. For example:
 - o An interim analysis indicates that participants have a lower rate of response to treatment than initially expected.
 - o Safety monitoring indicates that a particular side effect is more severe, or more frequent than initially expected.
 - o A paper is published from another study that shows that an arm of your research study is of no therapeutic value.
 - o Change in FDA safety labeling or withdrawal from marketing of a drug, device, or biologic used in a research protocol.
 - o Breach of confidentiality
 - o Change to the protocol taken without prior IRB review to eliminate apparent immediate hazard to a research participant.

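### The only open-ended adverse-event question is limited to concerns possibly related to the study, so off-checklist events that a participant does not link to it are not directly elicited

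*Combined protocol and SAP*

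**What the plan says.** Three statements set what must be captured. Section 4.2 says: "Any event that could be characterized by the definitions above is an AE whether or not considered related to the study or product". The definition above that sentence expressly takes in illness or injury arising during the study and the worsening of a condition already present. Section 4.3 says: "All adverse events occurring during each study period will be recorded". Under Reporting SAEs, section 4.5 says: "SAEs or SADR for Penn subjects regardless of attribution or expectedness will be submitted to the IRB within 10 days". The attribution scale in section 4.2 starts with a category for events with no causal link: "Unrelated - The AE is clearly NOT related to the intervention".

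Section 4.3 also sets how events are found, by two routes at each visit after Intake. The first is the side effects checklist: "The SEC will assess the frequency and severity of common side-effects associated with ramelteon or TN treatment". After listing the common and rare effects of ramelteon, the Potential Study Risks section adds: "All of these side effects shall be queried using a side effects checklist as described above". The second route is a non-structured question put by trained staff, with a one-week look-back, "to assess if participants are experiencing any additional symptoms or medical concerns that may be related to their participation in the study". Section 3.2 mentions the same kind of item under Side Effects: "An open-ended side effects question will also be included". The documents describe no open question that covers events of any cause.

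**The concern.** The definition and the recording duty place the judgement of cause after an event has been captured: the principal investigator (section 4.2) or the study physician (section 4.3) assigns it. The open-ended question, as its purpose is stated, brings part of that judgement forward to the moment of asking and leaves it with the participant. A fall, an infection or an emergency visit is just the kind of event that a participant may not connect with a sleep medicine or a nicotine patch, and such an event is unlikely to be on the checklist. If it is not mentioned, it never reaches the assessor and cannot enter the serious-event reporting rule. The adverse-event summaries in the progress reports to the funder (section 4.2) and in the annual data and safety monitoring report (section 4.5) would then fall short of the set of events that the protocol itself defines. The trial is also meant to lay the ground for a larger Phase IIb trial, so its safety record will be read again.

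**Working it through.** The point rests on comparing sections. Only one stated figure bears on it.

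1. **Frequency of asking.** Potential Study Risks states 16 side-effect assessments. The schedule of activities has 3 baseline and 5 quit-week visits in each of 2 periods: 2 × (3 + 5) = 16. The figure is reproduced. Participants are asked often enough; the question is what they are asked about.

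2. **What must be recorded.** All adverse events in each study period, whatever their cause (sections 4.2 and 4.3). Serious events go to the IRB whatever their attribution (section 4.5). An attribution category for unrelated events makes sense only if such events are collected.

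3. **What each route can find.**
   - *Checklist:* listed ramelteon and patch effects, including the rare ramelteon effects. No attribution by the participant is described, so a listed symptom is captured even if the participant blames something else. It does not reach events off the list.
   - *Open-ended question:* can reach off-list events, but is aimed at those that may be related to taking part.
   - *Examination:* provided for in section 4.3 where needed, but the schedule lists no physical examination after Intake.
   - *Blood pressure at every visit:* finds raised pressure only.
   - *Concomitant medication review:* finds an event only if it was treated with a medicine that the participant mentions.
   - *Written instruction to call between visits (section 3.2):* depends on the participant recognising a severe side effect or an adverse event.
   - *Ongoing chart review (section 4.1):* works on what is already in the chart.

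4. **Overlay.** Taking step 3 from step 2 leaves one class of event that no scheduled item directly asks about: those off the checklist that the participant does not link to the study. Illness, injury and medical care are the obvious members.

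5. **Effect on counts.** Let p be the true risk of an off-checklist event in a quit week and s the probability that it is reported. The recorded risk is p × s, and the share lost is 1 − s. For the two drug periods:
   - recorded difference = s_R × p_R − s_P × p_P
   - recorded ratio = (s_R / s_P) × (p_R / p_P)

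   If s_R = s_P = s, the difference becomes s × (p_R − p_P), which is smaller than the true one whenever s is below 1. The ratio is unchanged, and no difference appears where none exists. A false difference needs s_R and s_P to be unequal. The documents give no value for p or s, so no numerical size is offered.

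**The case against.** The strongest reply is that section 4.3 gives the purpose of the question and not its script. The form is not in the documents, and a threshold of possible relatedness is a low one. The same section has staff ask about a possible link to ramelteon or the patch after something has been reported, so relatedness is not settled wholly by the participant. It also opens by telling staff to seek information on adverse events, a term that section 4.2 defines without regard to cause. Visits fall on every weekday of the quit weeks, so an admission would probably show up as a missed visit. Withdrawal and affect scales at every visit after Intake, and a depression scale at set visits, pick up further symptoms.

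Much of this stands, and it limits the point. A reader might infer that every event a participant does not link to the study is lost. The documents do not support that: checklist symptoms, including the rare ramelteon effects, are rated without attribution, and the other routes will reveal some off-list events indirectly.

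The reply does not remove the mismatch. The stated purpose is what the form and the staff training can be expected to follow, and it filters on cause, however lightly. Follow-up questions about a report cannot recover an event that was not reported. None of the other routes asks about illness, injury or care as such.

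**Conclusion.** The stated scope of the only open-ended question is narrower than the protocol's own duty to record adverse events and report serious ones. The gap concerns off-checklist events that the participant does not link to the study, and the main consequence is under-counting in the adverse-event and serious-event reports. This assumes that the form follows the stated purpose of the question. The size is unknown, and no planned endpoint or analysis depends on it.

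A reader might also infer that the ramelteon-placebo comparison of adverse events will be biased, for instance because felt drug effects make participants readier to link other symptoms to the study in ramelteon weeks. That would need attribution to differ between periods. The trial is double-blind, each participant takes both treatments, and both quit weeks include the patch and attempted abstinence. Nothing in the documents shows that attribution would differ, so this is no more than a possibility. The Statistical Analysis section plans no such comparison; section 4.3 says only that checklist items can be summed to an index.

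**What to change.** In section 4.3, and in the matching open-ended item in section 3.2, have staff ask at each visit about any new or worsened symptom, illness, injury or medical care, whatever its cause. Delete the closing clause that limits the question to matters possibly related to taking part, and bring the open-ended form into line. Leave relatedness to the assessor already designated in sections 4.2 and 4.3. The checklist can stay as it is. The cost is one reworded sentence in each place and slightly more minor events to log; no visits, staff or procedures are added.

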4.4 Reporting of Serious Adverse Events and Unanticipated Problems

The following information about adverse events will be reported:

- Study Identifier
- Study Center
- Subject number
- A description of the event
- Date of onset
- Current status
- Whether study treatment was discontinued
- The reason why the event is classified as serious
- Investigator assessment of the association between the event and study treatment
- Welfare of subjects.

4.5 Investigator reporting: notifying the Penn IRB

This section describes the requirements for safety reporting by investigators who are Penn faculty, affiliated with a Penn research site, or otherwise responsible for safety reporting to the Penn IRB. The University of Pennsylvania IRB (Penn IRB) requires expedited reporting of those events related to study participation that are unforeseen and

indicate that participants or others are at increased risk of harm. The Penn IRB will not acknowledge safety reports or bulk adverse event submissions that do not meet the criteria outlined below. The Penn IRB requires researchers to submit reports of the following problems within 10 working days from the time the investigator becomes aware of the event:

- Any adverse event (regardless of whether the event is serious or non-serious, on-site or off-site) that occurs any time during or after the research study, which in the opinion of the principal investigator is: Unexpected (An event is “unexpected” when its specificity and severity are not accurately reflected in the protocol-related documents, such as the IRB-approved research protocol, any applicable investigator brochure, and the current IRB-approved informed consent document and other relevant sources of information, such as product labeling and package inserts.)

AND

Related to the research procedures (An event is “related to the research procedures” if in the opinion of the principal investigator or sponsor, the event was more likely than not to be caused by the research procedures.)

Reporting Process

Unanticipated problems posing risks to subjects or others as noted above will be reported to the Penn IRB using the form: “Unanticipated Problems Posing Risks to Subjects or Others Including Reportable Adverse Events” or as a written report of the event (including a description of the event with information regarding its fulfillment of the above criteria, follow-up/resolution and need for revision to consent form and/or other study documentation).

Copies of each report and documentation of IRB notification and receipt will be kept in the Clinical Investigator’s study file.

Reporting Deaths: more rapid reporting requirements

Concerning deaths that occur during the course of a research study, the following describes the more rapid reporting requirement of the Penn IRB for specific situations:

- Report the event within 24 hours when the death is unforeseen (unexpected) and indicates participants or others are at increased risk of harm.
- Report the event within 72 hours, for all other deaths, regardless of whether the death is related to study participation.

For reportable deaths, the initial submission to the Penn IRB may be made by contacting the IRB Director or Associate Director. The AE/Unanticipated Problem Form is required as a follow up to the initial submission.

Reporting SAEs

• Penn Subjects (including subjects at networks, affiliates or investigator-initiated sites); All on-site grade 3 or higher AEs or ADRs regardless of attribution or expectedness will be submitted to the IRB within 30 days. SAEs or SADR for Penn subjects regardless of attribution or expectedness will be submitted to the IRB within 10 days. Reports will continue to be sent to the IRB for 90 days following the last date the subject received study treatment/therapy or was exposed to an investigational device. All unexpected deaths or deaths related to the study agent(s)/device(s) must be reported within 24 hours. All other deaths should be reported within 30 days.

Other Reportable events:

- For clinical drug trials, the following events are also reportable to the Penn IRB:
- Any adverse experience that, even without detailed analysis, represents a serious unexpected adverse event that is rare in the absence of drug exposure (such as agranulocytosis, hepatic necrosis, Stevens-Johnson syndrome).
- Any adverse event that would cause the sponsor to modify the investigators brochure, protocol or informed consent form, or would prompt other action by the IRB to assure protection of human subjects.

- Information that indicates a change to the risks or potential benefits of the research, in terms of severity or frequency. For example:
 - o An interim analysis indicates that participants have a lower rate of response to treatment than initially expected.
 - o Safety monitoring indicates that a particular side effect is more severe, or more frequent than initially expected.
 - o A paper is published from another study that shows that an arm of your research study is of no therapeutic value.
 - o Change in FDA safety labeling or withdrawal from marketing of a drug, device, or biologic used in a research protocol.
 - o Breach of confidentiality
 - o Change to the protocol taken without prior IRB review to eliminate apparent immediate hazard to a research participant.
- Incarceration of a participant when the research was not previously approved under Subpart C and the investigator believes it is in the best interest of the subject to remain in the study.
- Complaint of a participant when the complaint indicates unexpected risks or the complaint cannot be resolved by the research team.
- **Exception:** A one time, intentional action or process that departs from the IRB and CTSRMC approved study protocol, intended for one occurrence. If the action disrupts the study progress, such that the study design or outcome (endpoints) may be compromised, or the action compromises the safety and welfare of study subjects, advance documented IRB approval is required.
- For exceptions on Industry or Cooperative group sponsored protocols, written approval must be obtained from the Sponsor prior to submitting your exception request to the IRB.
- For in-house studies with a Medical Monitor or Safety Monitoring Committee (not DSMB), approval must be obtained from the Medical Monitor or Safety Monitoring Committee prior to submitting your exception request to the IRB.
- **Deviation:** A one time, unintentional action or process that departs from the IRB approved study protocol, involving one incident and identified retrospectively, after the event occurred. If the impact on the protocol disrupts the study design, may affect the outcome (endpoints) or compromises the safety and welfare of the subjects, the deviation must be reported to the IRB within 10 business days.

Data, Safety and Monitoring Report. The PI will provide a summary of the DSM report on an annual basis as part of the progress report. The DSM report will include the expected versus actual recruitment rates, treatment retention rates, any quality assurance or regulatory issues that occurred during the past year, summary of AEs and SAEs, and any actions or changes with respect to the protocol.

Evidence of Training in Human Subject Research. All research personnel associated with this study have completed the CITI-Protection of Human Subjects Research Training as well as HIPAA Compliance Training.

5. Management of Information for Multi-center Research where a Penn Investigator is the Lead Investigator of a multi- center study, or Penn is the lead site in a multi-site study.

Not applicable

Risk/Benefit Assessment

The importance of this research outweighs the risks to subjects, which are minor. There is minimal risk for serious adverse events. The treatments and procedures used in this study have been shown to be relatively safe. Numerous clinical trials have demonstrated the safety and efficacy of ramlteon and TN. Research staff will monitor subjects closely during their participation. Data from this project will serve as preliminary data to formally test ramlteon as an adjunct behavioral component to smoking cessation treatment.

SUBJECT COMPENSATION

Participants will receive compensation at each session they attend and can receive up to \$592 for completing all study requirements (including travel reimbursement). Compensation distribution is shown in the table below.

Study Visit	Visit Compensation	Travel	Armband Incentive	Quit Incentive	Total
Intake*	\$20	\$10			\$30
Week 1 Baseline Session (Mon)	\$10	\$10			\$20
Week 1 Baseline Session (Wed)	\$10	\$10			\$20
Week 1 Baseline Session (Fri)	\$20	\$10	\$16		\$46
Week 2 Quit Assess. (Mon)	\$10	\$10		\$10 ⁺	\$30
Week 2 Quit Assess. (Tues)	\$10	\$10		\$10 ⁺	\$30
Week 2 Quit Assess. (Wed)	\$10	\$10		\$10 ⁺	\$30
Week 2 Quit Assess. (Thurs)	\$10	\$10		\$10 ⁺	\$30
Week 2 Quit Assess. (Fri)	\$10	\$10	\$20	\$10 ⁺	\$50
Week 5 Baseline Session (Mon)	\$10	\$10			\$20
Week 5 Baseline Session (Wed)	\$10	\$10			\$20
Week 5 Baseline Session (Fri)	\$20	\$10	\$16		\$46
Week 6 Quit Assess. (Mon)	\$10	\$10		\$10 ⁺	\$30
Week 6 Quit Assess. (Tues)	\$10	\$10		\$10 ⁺	\$30
Week 6 Quit Assess. (Wed)	\$10	\$10		\$10 ⁺	\$30
Week 6 Quit Assess. (Thurs)	\$10	\$10		\$10 ⁺	\$30
Week 6 Quit Assess. (Fri)	\$10	\$10	\$20+\$50 ^a	\$10 ⁺	\$100
TOTAL	\$200	\$170	\$122	\$100	
Grand Total:					\$592
* Participants who test positive for study prohibited drugs will not be eligible to receive visit or travel compensation.					
+ Participants will receive \$10/day (in cash) for each day of self-reported abstinence that is biochemically-confirmed					
^a Participants will be provided \$4/day for each day they wear the armband and complete the sleep diary plus \$50 if they provide at least 18 of 22 days of data (85%)					

INFORMED CONSENT

1. Consent Process

